5.1.3 Definition of dose-limiting toxicity

A DLT is defined as any toxicity not attributable to the disease or disease-related processes under investigation, which occurs from the first dose of study treatment (Day 1, Cycle 0) up to the last day of Cycle 1 (21 days after start of multiple dosing) in dose escalation cohorts and which includes, despite optimal therapeutic intervention:

- 1. Haematological toxicity \geq CTCAE (version 4) grade 4 present for more than 4 days
- 2. Non-haematological toxicity \geq CTCAE grade 3 including:
 - Infection including febrile neutropenia
 - Confirmed QTc prolongation (> 500 msec absolute or > 60msec above baseline)
- 3. Any other toxicity that:
 - is greater than that at baseline, is clinically significant and/or unacceptable, and is judged to be a DLT by the Safety Review Committee
 - that is a protocol defined stopping criteria (i.e. confirmed corneal ulceration)
 - results in a disruption of dosing schedule of more than 7 days

A DLT excludes:

- 1. Alopecia of any grade
- 2. Isolated laboratory changes of any grade without clinical sequelae or clinical significance

However, the incidence and type of DLT-type toxicity from Cycle 2 and beyond will be taken into account by the SRC in determining dose escalation steps.

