5.1.6 Toxicity management

If a patient experiences a CTCAE grade 3 and/or unacceptable toxicity including a DLT not attributable to the disease or disease-related processes under investigation, dosing will be interrupted and supportive therapy administered as required in accordance with local practice/guidelines. Patients with QTcF prolongation fulfilling the DLT criteria (i.e. confirmed QTcF prolongation to >500 msec absolute or a > 60 msec increase from baseline) should have study treatment interrupted and regular ECGs performed until resolution to baseline. If the QTc prolongation toxicity does not resolve to \leq grade 1 within 21 days the patient will be permanently withdrawn from study treatment.

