5.1.6.1 Escalation and expansion patients

[figure not shown]
If any other toxicity resolves or reverts to \leq CTCAE grade 2 within 21 days of onset and the patient is showing clinical benefit, treatment with AZD9291 may be restarted at the same dose or a lower dose using the rules below for dose modifications (see Figure 2) and agreement with the AstraZeneca Study Team Physician as needed.

[figure not shown]
If any other toxicity does not resolve to \leq CTCAE grade 2 after 21 days, then the patient should be withdrawn from the study and observed until resolution of the toxicity

On resolution of toxicity within 21 days:

- If a further episode of the same AE subsequently requires dose interruption, AZD9291 must restart at one dose level lower (unless in Cohort 1, when restart will be at Cohort 1 dose) on improvement of the AE.
- If a different AE subsequently requires dose interruption, AZD9291 may restart at the same or one dose level lower (unless in Cohort 1, when restart will be at Cohort 1 dose) on improvement of the AE at the discretion of the Investigator.

Patients who are at the lowest possible dose ie, who have their dose previously reduced to the Cohort 1 dose and who have demonstrated an acceptable response to the dose interruption may be permitted to restart at the lowest dose level at the discretion of the Investigator.

5.1.6.2 Phase II extension patients:

If any other toxicity resolves or reverts to \leq CTCAE grade 2 within 21 days of onset, treatment with AZD9291 may be restarted at the same dose (80 mg) or a lower dose (40 mg) following discussion and agreement with the AstraZeneca Study Team Physician as needed. There will be no individual modifications to dosing schedule in response to toxicity, only potential dose

reduction or dose interruption. If the toxicity does not resolve to \leq CTCAE grade 2 after 3 weeks, then the patient should be withdrawn from the study and observed until resolution of the toxicity.

On resolution of toxicity within 3 weeks:

• If an AE subsequently requires dose interruption, AZD9291 may restart at the same dose or the reduced dose, on resolution/improvement of the AE at the discretion of the Investigator.

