6.3.6 Ophthalmologic examination

Full ophthalmic assessment, including slit lamp examination, should be performed at screening and if a patient experiences any visual symptoms (including blurring of vision), with additional tests if clinically indicated. Any clinically significant findings, including those confirmed by the ophthalmologist must be reported as an AE. Photographs should be performed to record any clinically significant findings. These photographs should be available for central review by AZ and AZ representatives if necessary. Ophthalmology examination results should be collected in the eCRF.

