The grading scales found in the current National Cancer Institute CTCAE version 4 will be utilised for all events with an assigned CTCAE grading. For those events without assigned CTCAE grades, the recommendation in the CTCAE criteria that converts mild, moderate and severe events into CTCAE grades should be used. A copy of the current CTCAE version can be downloaded from the Cancer Therapy Evaluation Program website (http://ctep.cancer.gov).

Causality collection

The investigator will assess causal relationship between investigational product and each adverse event, and answer 'yes' or 'no' to the question: 'Do you consider that there is a reasonable possibility that the event may have been caused by the investigational product?'

For SAEs causal relationship will also be assessed for other medication and study procedure. Note that for SAEs that could be associated with any study procedure the causal relationship is implied as 'yes'.

A guide to the interpretation of the causality question is found in Appendix B of this Clinical Study Protocol.

Adverse events based on signs and symptoms

All AEs spontaneously reported by the patient or care provider or reported in response to the open question from the study personnel: 'Have you had any health problems since the previous visit/you were last asked?', or revealed by observation will be collected and recorded in the CRF. When collecting AEs, the recording of diagnoses is preferred (when possible) to recording a list of signs and symptoms. However, if a diagnosis is known and there are other signs or symptoms that are not generally part of the diagnosis, the diagnosis and each sign or symptom will be recorded separately.

Adverse events based on examinations and tests

The results from protocol mandated laboratory tests, vital signs, ECGs and other safety assessments will be summarised in the Clinical Study Report. Deterioration as compared to baseline in these parameters will therefore only be reported as AEs if they fulfil any of the criteria for a SAE, a DLT or are the reason for discontinuation of treatment with the investigational product unless clearly due to progression of disease under study (see Disease progression).

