If deterioration in a laboratory value, vital sign, ECG or other safety assessment is associated with clinical signs and symptoms, the sign or symptom will be reported as an AE and the associated laboratory result or other finding will be considered as additional information. Wherever possible the reporting investigator uses the clinical, rather than the laboratory term (eg, anaemia versus low haemoglobin value). In the absence of clinical signs and symptoms, clinically relevant deteriorations in non-mandated parameters should be reported as AE(s).

Deterioration of a laboratory value that is unequivocally due to disease progression should not be reported as an AE.

Any new or aggravated clinically relevant abnormal medical finding at a physical examination as compared with the baseline assessment will be reported as an AE.

Disease progression

Disease progression can be considered as a worsening of a patient's condition attributable to the disease for which the investigational product is being studied. It may be an increase in the severity of the disease under study and/or increases in the symptoms of the disease. The development of new, or progression of existing metastasis to the primary cancer under study should be considered as disease progression and not an AE. Events that are unequivocally due to disease progression should not be reported as AEs during the study.

New cancers

The development of a new cancer should be regarded as an AE and will generally meet at least one of the serious criteria. New cancers are those that are not the primary reason for the administration of the study treatment and have been identified after the patient's inclusion in this study. They do not include metastases of the original cancer.

Handling of deaths

All deaths that occur during the study, or within the follow-up period after the administration of the last dose of investigational product, should be reported as follows:

- Death, which is unequivocally due to disease progression, should be communicated to the study monitor at the next monitoring visit and should be documented in the CRF module, but should not be reported as a SAE during the study

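### An asymptomatic laboratory, vital-sign or ECG deterioration can interrupt dosing without being recorded as an AE, because Section 6.4.3 does not list interruption or reduction as a reporting trigger

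*Protocol*

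**What the plan says.** Section 6.4.3, under AEs based on examinations and tests, opens with "The results from protocol mandated laboratory tests, vital signs, ECGs and other safety assessments will be summarised in the Clinical Study Report". From this it concludes that deterioration in those results "will therefore only be reported as AEs if they fulfil any of the criteria for a SAE, a DLT or are the reason for discontinuation". Symptoms that accompany an abnormal result are AEs in their own right. For tests the protocol does not mandate, the same section makes a clinically relevant deterioration an AE even without symptoms.

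Section 5.1.3 defines a DLT as occurring "up to the last day of Cycle 1 (21 days after start of multiple dosing) in dose escalation cohorts". The criteria include haematological toxicity of grade 4 lasting more than 4 days, non-haematological toxicity of grade 3 or higher, confirmed QTc prolongation beyond stated limits, disruption of dosing for more than 7 days, and events the Safety Review Committee judges to be DLTs. Isolated laboratory changes without clinical sequelae or significance are excluded.

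Section 5.1.6, which covers all patients, interrupts dosing for grade 3 and/or unacceptable toxicity, including DLTs. Patients whose QTcF prolongation meets the DLT criteria "should have study treatment interrupted and regular ECGs performed until resolution to baseline". Section 5.1.6.1 then says: "If a further episode of the same AE subsequently requires dose interruption, AZD9291 must restart at one dose level lower". Section 6.3.3 asks for vital-sign changes to be recorded as AEs where applicable. Section 6.3.6 says of eye examinations: "Any clinically significant findings, including those confirmed by the ophthalmologist must be reported as an AE".

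**The concern.** The rule that stops dosing is wider than the rule that creates an AE. An asymptomatic abnormality can fall between them: significant enough to interrupt treatment, but neither serious, nor a DLT, nor the reason for discontinuation. Such an event has no AE entry, although Section 5.1.6.1 speaks of it as an AE.

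Safety and tolerability form part of the primary objective (Section 1.1) and are the primary endpoint for escalation and expansion (Section 7.1). Section 6.4.3 lists maximum grade, investigator causality, action taken with study drug and outcome as variables collected for each AE. Without an AE, the protocol names no place where the investigator's causality judgement and the dose action are tied to the abnormality. The AE summaries in Section 7.9, including the causally related and grade 3 or higher categories, would not contain the event.

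**Working it through.** The protocol gives no rate of asymptomatic abnormalities that alter dosing, so no under-count can be computed. The check is to run example events through the two rules. Each is assumed to be asymptomatic, non-serious, not due to the disease and not the reason for discontinuation. The broad reading of Section 6.4.3 treats the DLT criteria as thresholds that apply at any time. The narrow reading requires a DLT as defined in Section 5.1.3, inside its window.

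| Event | Dosing interrupted (5.1.6) | AE in escalation, Cycles 0–1 | AE in later cycles, expansion or extension |
|---|---|---|---|
| Grade 3 neutropenia, interruption of 7 days or less, not judged a DLT by the committee | Yes | No | No, on either reading |
| Grade 3 neutropenia, interruption of more than 7 days | Yes | Yes, by the disruption criterion* | Broad: yes. Narrow: no |
| Confirmed QTcF above 500 msec | Yes | Yes, by the QTc criterion | Broad: yes. Narrow: no |

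*Unless it is classed under the exclusion for isolated laboratory changes.

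**Row 1** does not depend on how the DLT criteria are read. Grade 3 is below the haematological threshold (grade 4 for more than 4 days), and an interruption of 7 days or less is below the disruption threshold (more than 7 days). None of the three routes in Section 6.4.3 is open, yet dosing was interrupted.

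**Rows 2 and 3** depend on what meeting the criteria for a DLT means once the DLT window has closed or never existed. Section 5.1.3 restricts DLTs to the escalation cohorts through Cycle 1 and speaks of DLT-type toxicity from Cycle 2, which favours the narrow reading. Section 5.1.6 uses the QTcF DLT criteria as thresholds for every patient, which favours the broad one. Two sites could record the same event differently.

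**Reach of the ambiguity.** Section 3.1 plans about 36 escalation, 162 expansion and 175 extension patients: 36 + 162 + 175 = 373. Those with no DLT window number 162 + 175 = 337, and 337/373 = 90%. The 36 escalation patients leave the window after Cycle 1. This shows how many patients the unclear wording covers, not how many events would be missed.

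**What remains in the report.** Section 7.3 assesses safety from laboratory, vital-sign and ECG data as well as AEs. Section 7.9 calculates CTCAE grades for laboratory variables and counts patients with at least one interruption or reduction. What is missing is the AE record that joins the abnormality to the dose change, with its causality entry.

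**The case against.** The strongest defence is that this is a deliberate and reasoned choice. Mandated results are summarised in full, so the protocol avoids reporting them a second time as AEs. Dose changes are counted under Exposure, and the review of other significant AEs in Section 7.3.1 takes in laboratory values and ECGs and names events leading to dose reduction. The CRF is not at hand and may capture a reason for each dose change. These points stand as far as they go: neither the abnormal value nor the dose change disappears. They do not restore the investigator's causality assessment or place the event in the AE tables, and the Section 7.3.1 review depends on sponsor judgement after the event.

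A reader might infer four stronger claims that the documents do not support.

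- **An extension patient with QTcF above 500 msec has no AE.** This holds only on the narrow reading, and Section 5.1.6 gives grounds for the broad one.
- **The primary safety endpoint under-counts toxicity, in 90% of patients.** Safety is assessed on more than AEs, and 90% describes scope only.
- **Section 6.3.6 contradicts Section 6.4.3.** The study plans schedule eye examinations only at screening. Later ones follow visual symptoms, which are reportable themselves, and Section 6.3.6 is a specific rule beside a general one. A cross-reference is enough.
- **The restart rule in Section 5.1.6.1 fails.** It does not require the first episode to have been entered as an AE, and Section 6.4.1 counts abnormal investigation results as AEs by definition. An investigator can recognise a recurrence from the clinical record. The mismatch is one of terms and reporting.

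**Conclusion.** The point holds as a gap in AE reporting. Under the protocol as written, at least one ordinary kind of event, short-lived asymptomatic grade 3 neutropenia, can interrupt dosing and leave no AE, with no causality or action-taken entry. For further events, the outcome outside Cycles 0 and 1 of escalation depends on a phrase that can be read two ways. The size of the effect is unknown and cannot be derived from the protocol. The conclusion assumes that sites apply Section 6.4.3 literally and that the Safety Review Committee has not judged the event a DLT. It does not show that the dose appears more tolerable than it is, because the abnormal values and dose changes are still reported. The point merits correction because the change is small and improves the attribution of dose changes.

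**What to change.** Amend Section 6.4.3 so that deterioration in a mandated test is reported as an AE when it meets SAE or DLT criteria or is the reason for interruption, reduction or discontinuation of the investigational product. State there that, for AE reporting, the DLT criteria apply in all cohorts and all cycles. Add cross-references to Sections 6.3.3 and 6.3.6 so that the vital-sign and ophthalmic instructions agree with the general rule. For patients already treated, query each recorded interruption or reduction that has no linked AE.

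The cost is a short protocol amendment, a CRF completion note and a round of data queries. Reported AE counts will rise somewhat. The change concerns reporting only and leaves every dosing and restart rule as it is.

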6.4.4 Reporting of serious adverse events

All SAEs have to be reported, whether or not considered causally related to the investigational product, or to the study procedure(s). All SAEs will be recorded in the CRF.

If any SAE occurs in the course of the study, then investigators or other site personnel inform appropriate AstraZeneca representatives immediately, or **no later than 24 hours** of when he or she becomes aware of it.

The designated AstraZeneca representative works with the investigator to ensure that all the necessary information is provided to the appropriate AstraZeneca patient safety data entry site within **one calendar day** of initial receipt for fatal and life threatening events and within **five calendar days** of initial receipt for all other SAEs.

For fatal or life-threatening adverse events where important or relevant information is missing, active follow-up is undertaken immediately. Investigators or other site personnel inform AstraZeneca representatives of any follow-up information on a previously reported SAE immediately, or **no later than 24 hours** of when he or she becomes aware of it.

Once the investigators or other site personnel indicate an AE is serious in the WBDC system, an automated email alert is sent to the designated AstraZeneca representative.

If the WBDC system is not available, then the investigator or other study site personnel reports a SAE to the appropriate AstraZeneca representative by telephone.

The AstraZeneca representative will advise the investigator/study site personnel how to proceed.

The reference document for definition of expectedness is Section 5.4 of the Investigators' Brochure for AZD9291.

6.5 Patient Reported Outcomes

Patient reported outcomes (PROs) is an umbrella term referring to all outcomes and symptoms that are directly reported by the patient. PROs have become a significant endpoint when evaluating effectiveness of treatments in clinical trials. The following PROs will be administered: EORTC QLQ C-30 and QLQ-LC13.

6.5.1 EORTC QLQ-C30 and QlQ-LC13

The EORTC QLQ-C30 was developed by the EORTC Quality of Life Group 1993. It consists of 30 items and measures cancer patients' functioning (HRQoL) and symptoms (Aaronson NK et al 1993). The QLQ-LC13 is a complementary module measuring lung cancer-associated symptoms and side-effects from conventional chemotherapy and radiotherapy (Bergman B et al 1994).

6.5.2 Administration of PROs

Questionnaires will be administered using paper questionnaires. The patient should complete the questionnaires at the scheduled clinic visit at screening, and every 6 weeks relative to the first dose of multiple dosing, discontinuation and progression as specified in the study plan (Table 2, Table 3 and Table 4). The patient should also complete a questionnaire progression. If any scheduled PRO assessment is not completed the reason for non-completion should be recorded.

PROs will be filled out prior to any other site activities and encounters with physician. The patients will be instructed to complete the PRO independently. This site will have a designated quiet space for patients to use when completing the assessments. Each centre should allocate responsibility for PRO assessment to a specified individual (e.g. a research nurse). The research nurse or appointed individual should stress the information is confidential.

It is important that the value and relevance of HRQoL data are explained carefully to participating patients so that they are motivated to comply with data collection. The research nurse or appointed individual should also stress that the information is confidential. Therefore, if the patient has any medical problems she should discuss them with the doctor or research nurse separately from their HRQoL assessment.

The instructions for completion of questionnaires are:

- It must be completed before any investigations or discussions about the status of the patient's disease with the clinic staff.
- The patient must complete it themselves without any intervention from family, friends, centre staff etc.
- The only exception to this is if the patient is blind or illiterate. In this case the questionnaire may be read to the patient verbatim, however the reader must not aid in the interpretation of questions or in the selection of answers.
- Only one answer to every question should be checked.
- Centre personnel should not review the responses to the questionnaire with the patient or with any other centre staff.

Following completion, the nurse or appointed individual may quickly scan the questionnaire visually for completeness and should confirm verbally with the patient that the questionnaire has been completed fully.

6.5.3 Cognitive patient interviews (optional)

Site staff in at least two countries will be asked to consent patients for optional interviews.

Patient contact information will be provided by site staff to an external CRO, Health Research Associates, Inc (HRA). The HRA interview study coordinator will contact patients by phone to schedule a date for the interview. Not all patients who consent may be able to participate. The goal is to conduct two interviews each (4-6 weeks and 4-6 months after treatment start, respectively) in approximately 50 patients and each interview will last 60 minutes.

Patients will be interviewed by trained qualitative interviewers who are experienced in qualitative research. All data will be confidential and the patient identifiers used will conform to applicable regulations, so as to preserve patient confidentiality (e.g., to assure matching between the audio recording and the subsequent transcript). Data from the audio recordings of the interviews will be transcribed to paper and analyzed using a number of qualitative techniques particular to this methodology (Ericsson 1980, Campanelli 1991). Due to the qualitative nature of the data and the analysis, the results will be presented in a separate report (i.e., not in the clinical study report) and the data (i.e., transcriptions) will not be entered into the study database.

Copies of the interview transcripts will be stored at HRA in locked files until they are packaged for storage in an off-site archive facility, where they will remain for a period of seven years and then be destroyed. Electronic files are all stored on password protected computers with routine back up onto a secure, firewalled server system. Individual files are password protected when shipped outside the secured server system. The voice files from the audio recordings are placed on a secure file transfer protocol (FTP) site where they can be accessed by password by the transcription vendor.

Should a patient withdraw from the study he/she will be asked if they are willing to participate in the follow-up interview.

